#### 2.8 Recruitment

In this study, patients who are decided to be discharged from the selected hospital and fulfilled the inclusion criteria will be recruited. The patients will be given a full explanation regarding the study according to the patient information sheet before enrolment. Subsequently, patients will be requested to provide written informed consent (Appendix C) if they agree to participate in the study.

# 2.9 Medication Reconciliation Upon Hospital Discharge

Medications in the discharge prescription will be considered as the primary source of reference for discharge reconciliation, as this is the list of medications that the pharmacy will refer to for medication preparation and eventually will be given to the patients upon discharge. Study pharmacists will conduct discharge medication reconciliation before randomization. Discharge medication reconciliation will be carried out by comparing the medications in the discharge prescription against the medications in the medication history assessment form (pre-admission medications) and inpatient medication charts (medications started during admission) to detect medication discrepancies before discharge medications preparation. If any differences are detected, study pharmacists will confirm with the doctor to decide intentional or unintentional medication discrepancies-any amendment to be documented on the discharge prescription.

# 2.10 Randomisation and blinding

The recruited patients will be randomised to the intervention and control groups in a 1: 1 ratio before discharge. Randomisation will be conducted using the online program available at http://www.graphpad.com/quickcalcs/index.cfm (12). A research coordinator will be appointed to administer the randomisation and inform the study pharmacist to deliver the intervention according to the assigned group. The research coordinator has no contact with patients, study pharmacists and doctors. In addition, the research coordinator will manage the

patient list with their code and group assignment. Subsequently, the research coordinator will send the patient list to the principal investigator to remind the patient of the follow-up date at the health clinic. Due to the nature of the intervention, patients, doctors, and study pharmacists are not blinded.

### 2.11 Intervention Group

MedBook Portal Notice will be attached in front of the patient's home-based medical card for the doctors and pharmacists at health clinics to identify the recruited patients. This appointment would be their first follow-up at health clinics after discharge from the hospital.

During the doctor's review of the patient in the intervention group, the doctor shall log in to the MedBook Portal to check on the discharge medication list and review the case based on the previous medical record in the home-based medical card and the discharge note if the patient hand over it to the doctors in their first review. Then, the doctor will conduct medication reconciliation by comparing the list of medications in the discharge prescription against the new prescription prepared.

Study pharmacists at the health clinics are required to screen patients' home-based medical cards presented to the pharmacy upon collecting medications. Once the pharmacists at health clinics identify the recruited patients via the MedBook Portal Notice, the pharmacist shall log in to the MedBook Portal to check the discharge medication list. The pharmacist shall conduct medication reconciliation by comparing the new prescription received against the discharge medication list in the portal. Intervention is to be carried out by the study pharmacists through confirmation with the doctor to determine the intentional or unintentional medication discrepancies.

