#### 2.4.1 Inclusion criteria

Patients who fulfil the following criteria will be invited to participate in the study:

- i. Adult patients aged 18 years and above in general medical wards who had any of the following comorbidities: (1) cardiovascular related diseases, e.g.: hypertension, acute coronary syndrome, heart failure, stroke, atrial fibrillation; (2) endocrine related diseases, e.g.: diabetes, thyroid disorders; (3) renal related diseases, e.g.: chronic kidney disease, end stage renal failure; (4) respiratory related diseases, e.g.: asthma, chronic obstructive pulmonary disease.
- ii. Patients who are referred to the selected primary health clinics after hospital discharge.
- iii. Patients with home-based medical card.

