#### 2.7.3 MedBook Portal Notice

A MedBook Portal Notice will be placed in front of the patient's home-based medical card. Only patients in the intervention group are given MedBook Portal Notice. Hence, the doctors and pharmacists at health clinics can identify the recruited patients in the intervention group. The layout of the MedBook Portal Notice is shown in Figure 2.4.

[figure not shown]

Figure 2.4: MedBook Portal Notice

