### 2.12 Control Group

Patients will receive the standard care in which doctors review patients based on the previous medical record in the home-based medical card and discharge note if the patient hands it to the doctors in their first review. Doctors cannot retrieve a patient's discharge medication list from MedBook Portal. No MedBook Portal Notice is attached to the patient's home-based medical card.

The principal investigator will provide a patient list in the control group to the study pharmacist at the health clinic. By knowing their appointment date, the study pharmacist shall search for the first prescription upon transitioning care from the hospital to the primary health clinic. Subsequently, the study pharmacist shall compare the discharge prescription in MedBook Portal with the first prescription to identify medication discrepancies. If any differences are detected, study pharmacists will confirm with the doctor to decide intentional or unintentional medication discrepancies. However, the study pharmacist might not be able to retrieve the first prescription immediately on the appointment date as there is no MedBook Portal Notice attached. As a result, the study pharmacist can only check with the prescriber on the discrepancy at a later time.

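### Clinic pharmacists find intervention patients by a Notice and control patients by a list; one list for both arms would be a minor, cheap improvement

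*Combined protocol and SAP*

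**What the plan says.** All references are to the combined protocol and SAP.

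- **Intervention arm (2.11).** Clinic pharmacists screen "home-based medical cards presented to the pharmacy upon collecting medications". The next step depends on the Notice: "Once the pharmacists at health clinics identify the recruited patients via the MedBook Portal Notice, the pharmacist shall log in to the MedBook Portal". They compare the new prescription with the discharge list, and "Intervention is to be carried out by the study pharmacists through confirmation with the doctor" to settle whether a difference was intended.
- **The Notice (2.7.3).** Only intervention patients receive it. "Hence, the doctors and pharmacists at health clinics can identify the recruited patients in the intervention group".
- **Control arm (2.12).** "The principal investigator will provide a patient list in the control group to the study pharmacist at the health clinic". The pharmacist then searches for the first prescription by appointment date. The section accepts that, with no Notice, "the study pharmacist might not be able to retrieve the first prescription immediately on the appointment date", and that "the study pharmacist can only check with the prescriber on the discrepancy at a later time".
- **Provisions that bear on retrieval.** "Patients with home-based medical card" is an inclusion criterion (2.4.1). Section 1.7 expects the personal record to be shown to the doctor at clinic follow-up. Section 2.7.2 tells doctors to log in at review and lets clinic pharmacists view both arms' discharge prescriptions. Section 2.10 sends the patient list to the principal investigator for reminders. Section 2.13 provides reminders and outcome collection at the first follow-up, neither limited by arm.
- **Outcome and analysis (2.14, 2.15).** The primary outcome is the percentage of first clinic prescriptions with a discrepancy. Categorical variables are compared by chi-square. Section 2.15 states no analysis set and no handling of missing outcomes.

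**The concern.** The Notice does two jobs. It prompts the clinic doctor to use the portal, which is the intervention. It also tells the clinic pharmacist whose prescription to collect, which is outcome ascertainment. If it is lost, detached or overlooked, the patient may miss both. Control retrieval does not depend on a card being shown.

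Missing primary outcomes could therefore depend on the arm and, within the intervention arm, on whether the intervention was delivered. Randomisation does not protect against loss that arises afterwards, a chi-square test on the retrieved prescriptions does not correct it, and a larger sample would not shrink it. Unless retrieval is reported by arm, a reader of the results could not judge it.

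**Working it through.** **1. Is a back-up written?** The plan gives no figure to reproduce here; this step is a check of the text. Each candidate has another stated use:

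- The portal view of both arms (2.7.2) is for comparing the two prescriptions. It is not written as a way to find who attended.
- The list held by the principal investigator (2.10) is for reminders. Section 2.12 passes clinics a control list only.
- Reminders (2.13) support attendance, not retrieval. The text does not say whether the pharmacist who sends them is at the hospital or the clinic.
- Owning a card (2.4.1) does not ensure that it is presented at the pharmacy with the Notice still attached and noticed.
- The doctor's log-in (2.7.2, 2.11) delivers the intervention. It does not direct the pharmacist to the prescription.

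So the routes differ, and the text shown has no written back-up. Figures 2.2 to 2.5 (portal screens, Notice, flow chart) are not shown, so one drawn there cannot be excluded.

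**2. How large could the bias be?** Inputs from section 2.5: control risk 49%, reduction 15 points (hence 34%), 161 per group. The 161 is taken as stated. Assumptions, because the documents give no values: m is the share of intervention patients not retrieved and r is their risk; retrieved intervention patients have 34%; all controls are found.

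- Observed difference = 49% − 34% = 15 points.
- Difference by assigned arm = 49% − [(1 − m) × 34% + m × r].
- Overstatement = m × (r − 34%).

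| Risk in missed patients (r) | m = 5% (about 8 of 161) | m = 10% (about 16 of 161) |
|---|---|---|
| 34% (full benefit anyway) | 0 | 0 |
| 41.5% (half the benefit) | 0.05 × 7.5 = 0.375 points | 0.10 × 7.5 = 0.75 points |
| 49% (no benefit) | 0.05 × 15 = 0.75 points | 0.10 × 15 = 1.5 points |

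In the last row the difference by assigned arm is 14.25 or 13.5 points instead of 15. The formula is linear in m, so 20% missed with no benefit would give 3.0 points.

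**3. Against sampling error.** SE = √[(0.49 × 0.51 + 0.34 × 0.66) / 161] = √(0.4743 / 161) = 5.43 points. With only 161(1 − m) intervention patients it is 5.49 points at 5% and 5.57 at 10%. The no-benefit row is then 0.75 / 5.49 = 0.14 and 1.5 / 5.57 = 0.27 of a standard error.

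**4. If controls are lost too.** Let control lose the same share, c = m. If the lost controls have average risk (49%), the overstatement is unchanged. It cancels when their risk equals [0.49 − (0.34 + D)(1 − c)] / c, where D is the difference by assigned arm:

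- r = 49%, 5% lost: (0.49 − 0.4825 × 0.95) / 0.05 = 63.25%.
- r = 49%, 10% lost: (0.49 − 0.475 × 0.90) / 0.10 = 62.5%.
- r = 41.5%, 5% lost: (0.49 − 0.48625 × 0.95) / 0.05 = 56.1%.
- r = 41.5%, 10% lost: (0.49 − 0.4825 × 0.90) / 0.10 = 55.75%.

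Above these values the bias reverses and the benefit is understated.

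**The case against.** The strongest reply is that this is a gap in wording with little practical weight. Most of it stands.

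- **The link between missed delivery and missed outcome is partial.** Doctor and pharmacist see the card at separate points (2.11). If only the pharmacist overlooks the Notice, the patient has still had the intervention, r stays near 34% and the bias is about nil. A value of 49% needs both to miss it.
- **The only retrieval difficulty the plan states is in control (2.12).** It describes delay rather than proven loss, but it means the case with all controls found cannot be treated as the expected one.
- **The limiting provisions are real.** The card is required, section 1.7 expects it to be shown, and 2.13 asks for outcome collection at first follow-up in both arms. An uncollected intervention prescription would depart from that intent. The means for a back-up already exist in the portal view and the principal investigator's list.

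What does not fall away is that sections 2.11 and 2.12, followed as written, use arm-specific routes to the primary outcome, and none of these provisions is stated as the way to recover a prescription when the Notice is unseen.

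A reader might also infer that a both-arm list should be barred from prompting any pharmacist query, to keep the intervention pure. The documents do not support that. Section 2.12 has list-found control discrepancies confirmed with the doctor, and Appendix B makes intent a required field. Barring the query in one arm would create a new asymmetry and limit what the pharmacist may do.

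**Conclusion.** The point holds as a minor, cheap improvement. Retrieval routes differ by arm, and the text shown has no written back-up for an intervention patient whose Notice is not seen. If 10% are missed with no benefit and all controls are found, the overstatement is 1.5 points, about a quarter of a standard error; with half the benefit it is 0.75 points. These sizes rest on assumed missed rates and on the planning risks of 49% and 34%.

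A reader might infer that intervention patients will be lost in numbers, or that the design favours MedBook. The documents support neither. They give no missed rate, several provisions limit the loss, and control prescriptions can be late or missed too, so the direction can reverse. Nothing here suggests that this gap alone would overturn the trial's conclusion.

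**What to change.** In 2.11 and 2.12:

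1. Have the principal investigator give each clinic pharmacist one list of all randomised patients due there, both arms, with appointment dates. The research coordinator already manages such a list (2.10).
2. Use it, with the same stated search window, to retrieve the first prescription in both arms. Keep the Notice as part of the intervention.
3. Analyse every retrieved prescription by assigned arm, whether or not the Notice was seen.
4. Report by arm the numbers listed, attending and retrieved.
5. Do not restrict pharmacist queries or reconciliation for list-found patients. Reconcile 2.11, 2.12 and the required intent field in Appendix B, so that a discrepancy found from the list is handled consistently in both arms.

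**Cost.** Protocol wording and more look-ups: 386 / 10 = 38.6 per clinic on average instead of 193 / 10 = 19.3, with no new visits. The load varies by site. From Tables 2.3 and 2.4, assuming an equal spread over each hospital's clinics, it runs from 64 / 2 = 32 (Sarikei) to 144 / 3 = 48 (Sarawak General). The other downside is that the list may prompt some extra reconciliation of intervention patients whose Notice was not seen; this should be recorded so that its extent can be reported.

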### 2.12 Control Group

Patients will receive the standard care in which doctors review patients based on the previous medical record in the home-based medical card and discharge note if the patient hands it to the doctors in their first review. Doctors cannot retrieve a patient's discharge medication list from MedBook Portal. No MedBook Portal Notice is attached to the patient's home-based medical card.

The principal investigator will provide a patient list in the control group to the study pharmacist at the health clinic. By knowing their appointment date, the study pharmacist shall search for the first prescription upon transitioning care from the hospital to the primary health clinic. Subsequently, the study pharmacist shall compare the discharge prescription in MedBook Portal with the first prescription to identify medication discrepancies. If any differences are detected, study pharmacists will confirm with the doctor to decide intentional or unintentional medication discrepancies. However, the study pharmacist might not be able to retrieve the first prescription immediately on the appointment date as there is no MedBook Portal Notice attached. As a result, the study pharmacist can only check with the prescriber on the discrepancy at a later time.

#### 2.13 Data Collection

The prevalence of medication discrepancies during discharge is collected through medication reconciliation by the study pharmacist at the hospital using the electronic data collection form. In addition, the type of medication discrepancies and predictors associated with medication discrepancies will be collected simultaneously using the first data collection form (Appendix A) by the study pharmacist at a hospital before allocation.

To compare the prevalence of medication discrepancies in the first prescription upon transition of care from hospitals to primary health clinics between the MedBook Portal and standard care,

data collection on the number of medication discrepancies will be carried out during the first follow-up at the health clinic after the hospital discharge. A pharmacist will administer the second data collection form (Appendix B) at the health clinic.

Throughout the study, there is only one follow-up visit at the health clinic, the first after hospital discharge. However, the time frame between the discharge date and the appointment date for the first follow-up at the health clinic varies from days to weeks depending on the duration determined by the hospital. Thus, the expected duration of subject participation would range from one week to two months.

To reduce loss to follow-up, the study pharmacist shall contact the patient via WhatsApp or phone call to remind the patient of the follow-up date at the health clinic. The schedule of enrolment, interventions and assessments of the study are presented in Table 2.5. The study flow chart is illustrated in Figure 2.5.

Table 2.5: Schedule of Enrolment, Interventions and Assessments

Timepoint	Study Period			
	Enrolment	Allocation	Post-	Close-out
			allocation	
	-tı	0	1 st Primary	
			Health Clinic	
			Follow Up	
ENROLMENT:				
Eligibility screen	X			
Participant	X			
Information Sheet				
Informed consent	X			
Allocation		X		
INTERVENTIONS:				
MedBook Portal		X	X	
ASSESSMENTS:				
Prevalence of	X		X	
medication				
discrepancies				
Predictors of	X		X	
medication				
discrepancies				

[figure not shown]

Figure 2.5: Study Flow Chart

### 2.14 Outcomes

The primary outcome of the study is the percentage of prescriptions with medication discrepancies in the first prescription during the first follow-up visit at the primary health clinic after hospital discharge. A comparison of the prevalence of prescriptions with medication discrepancies in the intervention group and the control group will be conducted.

The secondary outcome of the study is the percentage of prescriptions with medication discrepancies in the discharge prescription. This is measured before the intervention. In addition, the type of medication discrepancies and predictors associated with medication discrepancies in discharge prescriptions and the first prescriptions upon transitioning care from hospitals to primary health clinics will be collected. Predictors associated with medication discrepancies will be analysed using multiple logistic regression.

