To the best of our knowledge, there has been no study conducted in Malaysia, that aims to reduce the medication errors when patients were discharged from a tertiary or secondary hospital to primary health clinic. Past studies conducted in western countries provided limited generalizable evidence on the efficacy of their interventions in dealing with the problem in local context due to different healthcare delivery system and practices (5, 6). In addition, relevant studies conducted in Malaysia merely explore the prevalence and factors contributing to the problem and the perception of stakeholders on the feasibility of implementing medication reconciliation program upon hospital discharge (7, 8). Hence, this warrants the development of an effective measure to overcome the problem. Apart from exploring the prevalence and predictors of medication discrepancies upon discharge, an innovative intervention that aims to

reduce the medication discrepancies upon transition of care will also be introduced and implemented at the major divisions in Sarawak as our first move.

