### 1.5 Study Hypotheses

The study hypotheses are formulated based on the study specific objectives. For the first specific objective, the hypothesis is about the impact of MedBook Portal on the prevalence of medication discrepancies in the first prescription upon transition of care from hospitals to primary health clinics.

In terms of the second and third objectives, the hypotheses are based on the previous study conducted the hypotheses are based on the previous study conducted by Law and Chong (2017) in Malaysia. This study reported 49% of the discharge prescription were found to have a least one medication discrepancies (8).

For the fourth and fifth specific objectives, there are five variables are included as the secondary outcome of the study, namely age of patient, number of comorbidities, number of medications, type of medication (ATC categorization), and experience of prescriber (category of prescriber). All the five secondary outcomes are hypothesized to be the predictors of medication discrepancies. The hypotheses are tabulated in Table 1.1.

Table 1.1: Study Hypotheses

Specific objective 1: To assess the prevalence of medication discrepancies in the first prescription upon transition of care from hospitals to primary health clinics, comparing MedBook Portal to standard care.

H1a

There will be a significant difference of medication discrepancies rates between the intervention group and the control group after the intervention. The estimated difference of the medication discrepancies rates is 15%, with intervention group having lower medication discrepancies rates than control group.

Specific objective 2: To determine the prevalence of the type of medication discrepancies in the first prescription upon transition of care from hospitals to primary health clinics.

H2a

The prevalence of each type of medication discrepancy ranges from 5 - 60%, with Drug omission as the most common medication discrepancy in the first prescription upon transition of care from hospitals to primary health clinics.

Specific objective 3: To determine the prevalence of the type of medication discrepancies in discharge prescription.

Н3а

The prevalence of each type of medication discrepancy ranges from 5-60%, with Drug omission as the most common medication discrepancy in discharge prescription.

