# 2.2 Operational Definition of Terms

### 2.2.1 Medication Discrepancies

Medication discrepancy is defined as any variation or difference in medication regimen identified when comparing an old medication list and the newly prescribed medications.

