### 2.2.2 Intentional Medication Discrepancy

Intentional medication discrepancy is defined as a justified discrepancy by a change in the patient's clinical condition.

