# 2.2.3 Unintentional Medication Discrepancy

Unintentional medication discrepancy is defined as unjustified discrepancy after checking with prescriber. It is a medication error, specifically prescribing error.

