# 2.16 Chapter Summary

This is a two-group randomised controlled trial conducted at four public tertiary hospitals and ten public primary health clinics in Sarawak, Malaysia. Adult patients in general medical wards who are discharged from the hospitals and referred to the selected primary health clinics will be recruited in the study. Eligible subjects will be randomised into intervention group and control group in a ratio of 1:1. During the first follow-up at the primary health clinic after discharge from hospital, doctors in the primary health clinics review the patients in the intervention group based on the discharge medication list in the MedBook Portal. Patients in the control group receive the standard care. Study pharmacists conduct medication reconciliation and identify medication discrepancies.

The primary outcome of this study is the percentage of prescriptions with medication discrepancies in the first prescription during the first follow-up visit at the primary health clinic after hospital discharge. A comparison of the prevalence of prescriptions with medication discrepancies in the intervention group and the control group will be conducted. The secondary outcomes are the percentage of prescriptions with medication discrepancies in the discharge prescription, the type of medication discrepancies and predictors associated with medication discrepancies in discharge prescriptions and the first prescriptions upon transitioning care from hospitals to primary health clinics. All data will be analysed using The jamovi project (2022) (Version 2.3). All statistical tests are two-tailed and p<0.05 is set to be statistically significant.

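### The primary outcome counts justified changes while the intent tag goes unused, and the discharge form records only unintentional discrepancies under the same outcome name

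*Combined protocol and SAP*

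**What the plan says.** **Definitions.** Section 2.2.1: "Medication discrepancy is defined as any variation or difference in medication regimen identified" between an old list and the new prescription. Section 2.2.2: "Intentional medication discrepancy is defined as a justified discrepancy". Section 2.2.3 says of the unintentional kind alone: "It is a medication error, specifically prescribing error". In Table 2.2 the dose, frequency, omission and addition rows require only a difference from the discharge prescription; none mentions justification.

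**Primary outcome.** Section 2.14: "The primary outcome of the study is the percentage of prescriptions with medication discrepancies in the first prescription", at the first clinic visit. Section 2.16 repeats it: "The primary outcome of this study is the percentage of prescriptions with medication discrepancies in the first prescription". Neither adds a qualifier.

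**Intent at the clinic.** Sections 2.11 and 2.12 have the study pharmacist settle intent with the doctor in both arms, and Appendix B makes the intentional/unintentional tag a required item for each drug.

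**Discharge outcome.** Section 2.14 names it with the same unqualified term. Section 2.9 has the pharmacist decide intent at discharge, and 2.13 says the prevalence, types and predictors come from the hospital form. In Appendix A, the legible drug-name items and the items asking for further discrepancies are worded for unintentional discrepancies only.

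**Planning rate.** Section 1.5: "This study reported 49% of the discharge prescription were found to have a least one medication discrepancies". Section 2.5 uses this 49% with a reduction of 15 points. Neither section says which class of discrepancy the figure covers.

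**The concern.** There are two separate problems.

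The first concerns how the primary result can be read. If the plan is followed exactly, a clinic prescription altered for a good clinical reason is an event, just like a prescribing error. A fall in the total could come from fewer errors, fewer justified changes, or both. The information that separates these is collected for every drug but has no planned use. If an unintentional-only result appears later, nobody can tell whether it was chosen after the data were seen, and 2.10 says doctors and study pharmacists are unblinded.

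The second is that the discharge outcome cannot be obtained as written. The form named as its source holds only one of the two classes. Discharge prevalence, types (objective iii) and predictors (objective v) would be unintentional-only. The clinic counterparts (objectives ii and iv) would cover any discrepancy. All would carry one name. Table 1.1 sets the two time points out in parallel: H3a gives a range of 5 to 60% "with Drug omission as the most common medication discrepancy in discharge prescription", and H2a gives the same range and the same leading type for the clinic.

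**Working it through.** **Step 1. What each source can deliver.**

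| Item | Term in 2.14 | Form | Class recorded |
|---|---|---|---|
| Clinic prevalence (primary), types, predictors | unqualified, so any (2.2.1) | Appendix B | both, tagged |
| Discharge prevalence, types, predictors | unqualified, so any (2.2.1) | Appendix A | unintentional only |

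The clinic row is consistent, and both classes can be recovered from it. The discharge row is not: the form lacks the intentional class. The first items of Appendix A and Figures 2.1 and 2.5 are not legible in the copy reviewed. The legible items run from clinic of referral (item 5) through comorbidities, number of medications and prescriber (items 6 to 8) to the discrepancy items, which already say unintentional.

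**Step 2. Role of the tag.** Section 2.14 lists no outcome by intent. Section 2.15 gives chi-square tests for categorical variables and logistic regression for predictors, with no restriction, secondary comparison or sensitivity analysis by intent.

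**Step 3. The plan's own figure.** Inputs from 2.5: 49% v 34%, two-sided 5%, 80% power, 161 per arm. The pooled formula is

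n = [1.96·√(2·0.415·0.585) + 0.84·√(0.49·0.51 + 0.34·0.66)]² / 0.15²

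With unrounded normal quantiles this gives 168.2, so 169 per arm. The unpooled version gives 165.5, so 166. The stated 161 is therefore slightly low. Exact enumeration of the chi-square test without continuity correction at 161 per arm gives power 0.779, or 78%. That small gap is a separate matter; 78% is the reference below.

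**Step 4. If 49% and 34% are unintentional rates and the outcome is any discrepancy.** Assume justified changes occur independently of errors on a share q of prescriptions (q is not in the documents). Control rate = 1 − 0.51(1 − q). Intervention rate = 1 − 0.66(1 − q) if the portal leaves justified changes alone, or 1 − 0.66(1 − q·34/49) if it lowers them in the same proportion as errors.

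| q | Control | Intervention, unaffected | Difference (points) | Power | Intervention, proportional | Difference (points) | Power |
|---|---|---|---|---|---|---|---|
| 10% | 54.1% | 40.6% | 13.5 | 68% | 38.6% | 15.5 | 80% |
| 20% | 59.2% | 47.2% | 12.0 | 58% | 43.2% | 16.0 | 83% |
| 30% | 64.3% | 53.8% | 10.5 | 48% | 47.7% | 16.6 | 85% |

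**Step 5. If 49% is an any-discrepancy rate and the outcome is unintentional only.** Assume a share s of the affected prescriptions have justified changes only (s is not in the documents). Control rate = 0.49(1 − s). Intervention rate = 0.34(1 − s) if the relative effect is kept, or the control rate minus 0.15 if the absolute 15 points of H1a is kept.

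| s | Control | Same relative effect | Power | Same 15 points | Power |
|---|---|---|---|---|---|
| 10% | 44.1% | 30.6% | 71% | 29.1% | 80% |
| 30% | 34.3% | 23.8% | 55% | 19.3% | 87% |
| 50% | 24.5% | 17.0% | 38% | 9.5% | 96% |

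The choice of class can move power well below or well above 78%. The documents do not say which case applies.

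**The case against.** The strongest reply is that an any-discrepancy primary is deliberate and coherent. The research question, objectives, H1a, conceptual framework and 2.14 all speak of discrepancies, and 2.2.1 defines the word. Both arms use the same form. The class also does not depend on the prescriber's account of intent, which is given unblinded (2.10) and may be sought later in controls (2.12). This stands. It settles neither the unused tag nor the mismatch between Appendix A and 2.14.

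A reader might go further in four ways that the documents do not support.

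- *That the primary outcome contradicts the study's aim.* Section 1.2 does describe the gap as the lack of a study "that aims to reduce the medication errors when patients were discharged from a tertiary or secondary hospital to primary health clinic". But that describes the literature, and the same section ends by giving this study's intervention the aim of reducing discrepancies.
- *That a discharge-to-clinic comparison is biased.* The plan never makes that comparison; its one stated contrast is between arms. The two measures also use different reference lists by design (Tables 2.1 and 2.2).
- *That the trial is underpowered because of the definition.* Steps 4 and 5 run in both directions.
- *That arm-dependent tagging distorts the primary result.* As written, the primary outcome does not use the tag. This is a caution for an unintentional-only analysis, not a fault in the present primary.

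**Conclusion.** The point holds in two parts. First, the primary outcome includes justified changes. That is a legitimate choice, but by itself it cannot show whether errors fall, and the tag that could show it has no pre-specified use. Second, the discharge outcome, its types and its predictors cannot be obtained as 2.14 words them from the form that 2.13 names; the plan would report an unintentional-only figure under an any-discrepancy name. The second part is an inconsistency in the text and needs no assumption beyond the legible Appendix A items being representative of that form.

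The numerical effect is not determined. Against 78% power for 49% v 34% at 161 per arm, the scenarios give 48% to 85% for any discrepancy and 38% to 96% for unintentional only. These rest on assumed values of q (10 to 30%) and s (10 to 50%), on independence of justified changes and errors in Step 4, and on how the portal's effect carries over. Which class should be primary is a trade-off for the sponsor. The plan should be corrected before analysis; because Appendix B holds the tag, both clinic results remain recoverable.

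**What to change.** 1. In 2.14, state that the primary outcome is any discrepancy as defined in 2.2.1 or, if the sponsor meant unintentional discrepancies, say so before analysis. In 2.15, pre-specify the between-arm comparison of the other class from the Appendix B tag, always reported beside the primary. Add a note that the tag rests on an unblinded prescriber's answer that may come later in controls (2.10, 2.12).
2. Reconcile Appendix A with 2.14 by one of two routes. Either relabel the discharge outcome, types and predictors as unintentional, and also report clinic types and predictors for that class. Or, if data collection is still open, record both classes with the tag in Appendix A; 2.9 already has the pharmacist decide intent.
3. In 2.5, state which class the 49% and the 15 points refer to.

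The cost is wording in 2.5, 2.14 and 2.15, one extra pre-specified analysis, and either a relabelled secondary outcome with clinic results also shown for the unintentional class, or an added item on the hospital form. No new clinic data are needed.
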